## 8.7 Please attach study design/subject visit schedule here:

Name
PNS+PT Visit Schedule Table (06-14-2017) | History

Description

If you have an electronic schedule of study visits and/or procedures please attach here.

View: 09-00 Inclusion/Exclusion Criteria

### 9.0 Inclusion/Exclusion Criteria:

### 9.1 What are the inclusion criteria? Put this information in bullet form:

- shoulder pain localized to the glenohumeral joint, subacromial area or deltoid insertion associated with: a) rest; b) passive abduction or external rotation range of motion (ROM); c) active abduction ROM; or, d) manual palpation;
- shoulder pain onset or worsening after the most recent stroke;
- weakness of shoulder abductors (≤4/5 on MRC if isolated movement is present);
- $\geq$  21-yrs old;  $\leq$  90-yrs old;
- time of stroke  $\geq$  3-mo;
- duration of HSP ≥3-mo;
- HSP with moderate to severe pain (BPI SF- $3 \ge 4$ );
- cognitive and communication ability to fulfill study requirements (cognitive ability based upon a score of ≥24 on the Mini Mental Status Exam (MMSE));
- availability of reliable adult who can assist with study procedures if necessary;
- willing and able to report shoulder pain and other conditions and complete study visits throughout the 7 month study period.

#### 9.2 What are exclusion criteria? Put this information in bullet form:

- joint or overlying skin infection or history of recurrent skin infections;
- insensate skin;
- need to take > 1 opioid and > 1 nonopioid analgesic medication for HSP;
- regular intake of pain medications for another chronic pain;
- botox injection or subacromial steroid injections to the shoulder within the past

Please list inclusion criteria.

Please list exclusion criteria.

#### 12 wks:

- receiving OT or PT for HSP;
- bleeding disorder or INR > 3.0;
- sensitivity to skin surface electrodes and/or medical-grade adhesives, gels, tapes;
- medical instability;
- pregnancy;
- uncontrolled seizures (>1/mo for 6-mo);
- history of cardiac arrhythmia with hemodynamic instability;
- history of lidocaine allergy;
- history of Parkinson's disease, SCI, TBI, MS, or ipsilateral UE lower motor neuron lesion;
- history of complex regional pain syndrome, myofacial pain syndrome, other pain conditions (investigator discretion);
- cardiac pacemaker or other implanted electronic device;
- history of valvular heart disease (artificial valves, requiring antibiotics for procedures, etc.);
- severely impaired communication;
- history of compromised immune system (i.e., recently or actively taking immunosuppressive therapies, AIDS) congenital immunodeficiency, or any other cause for compromised immune system with which participation would pose excessive risk.

## 9.3 How will subject eligibility be determined and by whom?

Subject eligibility will be initially assessed by the study coordinator and will be confirmed and reviewed by the Investigator. Eligibility will be determined from:

- review of medical history available in the chart;
- completion of the Brief Pain Inventory Short Form (to confirm baseline degree of pain of  $\geq 4$ );
- bloodwork (to confirm suitable coagulation levels in patients on anticoagulants) or pregnancy urine or serum test in applicable female subjects;
- physical examination of shoulder.

## 9.4 Will you exclude women and minorities, or persons under 21 from enrollment? Yes

9.5 If yes, which groups are you excluding? Provide justification for your decision. Pregnant women: Pregnant women will be excluded since the effect of electrical stimulation on the fetus is not known.

Persons under 21: Children are excluded based on scientific considerations as they represent a fundamentally different population with chronic post-stroke shoulder pain etiologies and substantially different from the adult population. Individuals that are at least 21 years of age possess additional maturity beyond those that are 18. The study involves the use of an external stimulator and requires the maintenance of a percutaneous exit site. As such, we believe that this additional level of maturity is a valid reason to extend the minimum age of enrollment to 21.

### 9.6 Attach Documents:

Name Description

There are no items to display

View: 10-00 Risk/Benefits

## 10.0 Assessment of Risk I:

- 10.1 Identify and distinguish between those procedures that are standard versus those that are experimental. Include the frequency and duration of each activity and the total length of subject participation:
  - Physical Exam and Range of Motion of shoulder (standard): A physical exam and range of motion assessment is standard for patients with shoulder pain and will be done at Visit 1. The shoulder will be physically inspected during each visit.
  - Collection of bloodwork (standard): The blood test (INR score) is standard for patients taking anticoagulants. This test will be collected in applicable subjects at Visit 1. A pregnancy test will also be administered in applicable subjects and can either be urine or serum pregnancy test.

Please describe in detail.

Check yes or no.

List groups to be excluded then provide justification.

If you are unable to fit your answers in the text boxes provided please attach as a word document.

Please distinguish between those procedures that are standard versus those that are experimental. Describe in detail all experimental procedures.

- EMG needle electrode testing (experimental): EMG needles are commonly used to evaluate muscle physiology and strength of muscle contractions. In this study, however, EMG needle (Sprint Test Needle) testing will be used to deliver test stimulation during the lead implant procedure.
- Placement of Percutaneous Fine Wire Intramuscular Lead (experimental): The placement of the lead during the lead implant procedure and the use of stimulation during the treatment phase are experimental. Local anesthetic will be used.
- X-rays (standard): One 2-view (AP/Lateral and Scapular Y) shoulder x-ray will be conducted following the removal (explant) of the electrode lead, to determine and document the presence of any retained fragments.
- Physical Therapy: Standard PT (standard) will be used during the treatment phase for the active PT groups. For the sham PT group (experimental), sham ultrasound therapy and light application of inert gel to the shoulder will be utilized, but standard PT not expected to affect outcomes related to shoulder function will be utilized as well. There are 8 PT Visits.
- Collection of surveys and questionnaires BPI, SF-36 (standard): These surveys are used for research, but are commonly used in pain patients. These surveys will be collected as defined elsewhere in this protocol for 9 Outcomes Assessments Visits; the BPI additionally is collected at the Start of Stimulation Visit. The Mini Mental Status Exam (MMSE, also standard) will be collected at Visit 1. The BDI and PCS (also standard) are used for research, but are commonly used in pain patients. They will be collected at Visit 1. The FABQ (experimental) will be collected at Visit 1. The PGIC (experimental) will be collected at Visit 12.
- Fugl-Meyer Motor Assessment (upper limb): The FMA (standard) will be used as defined elsewhere in this protocol for 4 Outcomes Assessments Visits.
- Other outcomes measures (experimental): Isometric voluntary abduction shoulder torque (IVAST), shoulder kinematic analysis, and measures of central sensitization (mechanical pain thresholds for hyperalgesia, pinprick pain thresholds for hyperalgesia, temporal summation of repetitive pin-prick stimuli) are used for research but some also are used in clinical practice as well. They will be used as defined elsewhere in this protocol for 4 Outcomes Assessments Visits.
- 10.2 Describe any therapeutic alternatives to the research that may exist. How are they different from those procedures that subjects would normally undergo? Numerous interventions exist for the treatment of shoulder pain following stroke. This is due to the large number of possible etiologies, the diversity of clinicians that treat stroke patients, and the lack of consensus regarding a standard of care. None of the following interventions have been shown to reduce pain reliably in randomized controlled trials.

Slings and other supports: Arm slings and other mechanical supports, such as wheelchair trays, are often used to support the forearm and distribute its weight to one or both shoulders in an effort to prevent or reduce subluxation. Although slings may reduce subluxation, they often fail to reduce shoulder pain as subluxation recurs once they are removed and may slow rehabilitation by reducing arm mobility.

Strapping: Strapping is the application of non-stretch tape to the affected limb to support the glenohumeral joint while allowing free movement of the arm. In a randomized controlled study of 33 patients, those who received strapping reported reduced average pain compared to those who received no therapy (inactive control group). However, strapping fails to produce a significant benefit compared to active control groups, who received either sham strapping or standard physiotherapy without strapping. In addition, the tapes must be replaced at least every three days, and skin irritation is common.

Local Injection Techniques: Corticosteroid injections address pain by treating inflammation. Approximately 50% of clinicians who treat patients with poststroke shoulder pain believe that steroid injections are effective. However, there are only two randomized controlled trials of corticosteroid injections for the treatment of post-stroke shoulder pain and they have mixed results. A recent trial of subacromial injections reported significant benefit over placebo. However, an earlier placebo controlled trial of intra-articular injections showed no benefit. Post-stroke shoulder pain has a variety of possible etiologies and does

Describe any therapeutic alternatives. Can subjects receive this drug or device outside of a research study?

not always arise from inflammation, explaining why steroid injections do not consistently outperform placebo in stroke patients. In addition to uncertain efficacy, repeat corticosteroid injections are associated with frequent adverse events, making them a poor treatment option.

Botulinum toxin causes local paresis of muscles by blocking cholinergic transmission at the neuromuscular junction. It has been widely used to treat spasticity and some data suggest that it may also help to relieve pain. Six of nine patients in a small uncontrolled study receiving an injection of botulinum toxin to the affected limb reported pain reduction. However, the effect of botulinum toxin is known to diminish after 3-4 months, making repeated injections necessary. Little data exist regarding the repeated use of botulinum toxin for shoulder pain relief.

Oral analgesic medications: The use of opioid and nonopioid analgesics, including nonsteroidal anti-inflammatory drugs (NSAIDs) to manage shoulder pain is common practice. Unfortunately, extended use of opioids can lead to dependence and side effects such as headache, skin rash, dizziness, and gastrointestinal symptoms. Though NSAIDs may reduce shoulder pain in the general population, their efficacy has not been demonstrated in the stroke population.

Therapeutic exercises: Therapeutic exercises under the supervision of a trained professional are generally considered to be an important part of poststroke rehabilitation. Although they prevent immobility and improve the range of motion (ROM) of the hemiplegic arm, studies have found that some exercises, such as the use of an overhead pulley, can cause soft tissue damage and thereby worsen shoulder pain. In fact, exercises are generally associated with a worsening of pain or no change, rather than an improvement. In a study investigating static positional stretches, the treatment group showed increasing levels of pain.

Acupuncture/Electroacupuncture: Acupuncture has been used for centuries to treat various types of pain and is believed to improve cutaneous and muscle blood flow and to increase pain thresholds. Electroacupuncture, a therapy in which traditional acupuncture needles are used in conjunction with electrical stimulation, has been evaluated as a therapy for shoulder pain in post-stroke subjects in a randomized study comparing electroacupuncture plus occupational/physical therapy to therapy alone. Although statistically significant improvements in pain reported via a Visual Analog Scale were observed in the treatment group, the study did not follow the group beyond the conclusion of the treatment. Thus it is not clear how often the therapy must be reapplied. In addition, electroacupuncture requires repeated clinic visits (at least 3 visits per week for 1 month). Traditional acupuncture has also been evaluated as a treatment for shoulder pain; however subjects in these studies had non-stroke shoulder pain etiologies.

Surface electrical stimulation: Surface electrical stimulation uses skin surface electrodes applied to the shoulder to deliver stimulation from an external stimulator. Baker and Parker published the first results from a randomized controlled trial of surface electrical stimulation for the treatment of poststroke shoulder pain. The authors found a treatment effect for subluxation but inconclusive results regarding pain relief. The investigators of a later study hoped to obtain more conclusive results than Baker and Parker by enrolling a larger population of 120 and following the subjects for two years. Pain was noted as present or absent at rest during passive motion and during active motion. Subjects were also asked to rate their pain using a visual analogue scale (VAS). For a subject to be classified as having no pain, all four variables had to be negative. A significantly higher proportion of subjects receiving electrical stimulation had no pain at 3, 6, 12, and 24 months compared to the control group (80.7% vs. 55.1%, p<0.01). The treatment subjects also showed a greater reduction in subluxation and a significant improvement in the recovery of arm motion.

The results of four additional studies investigating surface electrical stimulation are summarized in a Cochrane review. Although the authors found a significant improvement in pain-free range of motion (ROM) in the treatment groups, the data did not support a significant reduction in pain intensity or incidence. The authors concluded that larger randomized controlled studies would be necessary to fully examine the effects of electrical stimulation in the post-stroke shoulder pain population.

Another literature review including six trials found that electrical stimulation paired with conventional therapy is not superior to conventional therapy alone for pain prevention. However, they noted that this may be due to the indirect way in which most studies measured pain (as "pain-free range of shoulder external rotation"). When pain was measured directly, using a VAS, electrical stimulation was found to be more effective in preventing pain than conventional therapy.

The results regarding the efficacy of surface electrical stimulation as a treatment for post-stroke shoulder pain have been promising, leading to its recommendation by several recently published guidelines. In addition, a literature review proposed that surface electrical stimulation combined with gentle clinician guided exercises should be considered the "best practice" for acute stroke survivors. However, several authors have noted that even with further evidence of the efficacy of surface electrical stimulation, it is unlikely that it will ever be the standard of care due to the discomfort caused by stimulation of cutaneous pain receptors, the potential for skin irritation under multiple surface electrodes, the need for skilled personnel to place the surface electrodes on a daily basis, and muscle fatigue that commonly occurs due to the high frequency of stimulation. Baker and Parker noted that either an implantable or a percutaneous system would have to be developed before electrical stimulation could become the preferred treatment. For these reasons, researchers have turned their attention to the use of intramuscular electrical stimulation.

bion® microstimulator (investigational): Due to the effectiveness of electrical stimulation but the difficulties associated with surface electrical stimulation, researchers have begun to investigate direct muscle and nerve stimulation. The bion® microstimulator used by Bioness, Inc. (Valencia, CA), is currently being investigated for the treatment of post-stroke shoulder pain and subluxation. Although the bion has technical advantages, including its small size and selfcontained electrode, it also suffers from considerable disadvantages. First, the device does not utilize a trial stage to evaluate whether a candidate is likely to experience pain relief from long term use prior to implantation. Second, implantation of the bion requires fluoroscopy and precise placement in close proximity to the deep axillary nerve trunk. Third, the device must be recharged daily using a large, stationary charging apparatus, to which the patient must be tethered during the recharging session. In addition, the bion's extraction requires open surgery. Finally, the bion requires precise placement due to its bipolar configuration, as the stimulus current density (and efficiency of nerve recruitment) drops off rapidly with distance from the target nerve. Even a small migration of the bion could significantly diminish its effectiveness. Data regarding the safe and effective use of the bion for post-stroke shoulder pain have not yet been published.

10.3 What are the outcome variables and how will they be analyzed? What are the statistical and analytical methods that will be used? Note this section can be copied from the NIH Grant Application or from the Statistical and Analytical Methods section of the industry trial protocol.

See attachments below.

Define outcomes and describe data analysis, please include a power calculation.

10.4 If the above requested information does not fit in the text box please attach a word document here:

If the requested information does not fit in the text box please attach a word document.

Name Description

Data Analysis (inc. Sample Size Calculation under Expectations and Analysis, Aim 1) | History
Outcomes Measures | History
Revised Sample Size Wilson PNS+PT R01 (2016 10 12) | History

View: 10-01 Risk/Benefits

#### 10.1 Assessment of Risk II:

10.5 List and quantitate the risks involved for each experimental procedure in bullet form. Identify risks as common (greater than 10%) uncommon (greater than 1% up to and including 10 %) rare (1% or less). This must match the risks listed in the Consent Form:

1) Risks associated with needle insertion for Sprint MicroLead placement

There are minor risks associated with inserting a Lead through the skin with a needle. These risks are similar to the risks of any needle injection including the possibilities of puncturing a blood vessel, irritating a nerve, and temporary bruising or pain at the insertion site. The risks of puncturing a blood vessel and irritating a nerve are uncommon, but the risks of temporary bruising and pain at the insertion site are common.

Some participants may experience a vasovagal ("fainting") response due to the discomfort or anxiety associated with of the procedure, especially among those with prior history of "fainting." This risk is rare and may be associated with symptoms of lightheadedness, dizziness and or diaphoresis with concomitant reduction in blood pressure and heart rate. For those with prior history of "fainting" the procedure will be performed with the subject in the lateral decubitus position.

To minimize the risks associated with percutaneously placing fine wire leads, only appropriately trained physician investigators will perform the procedure. In addition, the risk of excessive bleeding will be reduced by excluding candidates who are taking warfarin with an INR > 3.0 and by placing manual pressure on the implantation site until hemostasis is achieved. Finally, the risk of discomfort during the procedure will be reduced by the use of an appropriate amount of local anesthetic.

It is possible that, in some cases, multiple attempts may be required to achieve appropriate placement of the Lead during the procedure. Each additional attempt at Lead placement carries the same risks as the initial attempt described in this section.

2) Risk of skin irritation, infection, or inflammation at the Sprint MicroLead exit site

There are risks of leaving a Sprint MicroLead in place for 4 weeks, including skin irritation, infection, and granuloma formation (mild tissue inflammation) at the Lead exit site. Symptoms include redness, swelling, or pain. The risk of skin irritation is common while the risks of infection and granuloma formation are rare.

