## 4) Risk of infection associated with retained Sprint MicroLead fragments

A Lead fragment could result in the formation of a granuloma or infection. Although the occurrence of a fragment-related infection or granuloma is uncommon an infection may require removal of the Lead fragment and/or treatment with antibiotics. Investigators at the Cleveland FES Center and Case Western Reserve University have over 30 years of experience with dozens of research participants and hundreds of implanted leads like those used in this study. Infections and granulomas of leads or lead fragments have been uncommon, which is attributed to the materials and procedures that have been developed as well as the extensive experience of the Investigators..

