The 32 subjects randomized to the treatment group each had four percutaneous leads placed that were identical to the Smartpatch Lead. The lead placement procedure was well tolerated. All leads remained intact and free of infection during the 7-week indwelling period. Of the 128 leads placed in this study, the tips of five leads (3.9%) among four subjects (12.5%) broke during removal, none of which resulted in an adverse event. Granuloma formation defined as localized tissue inflammation exhibited by redness, swelling, or pain at the lead exit site was noted for five leads (3.9%) in two subjects (6.3%). All granulomas resolved after lead removal with no further intervention required.

The authors concluded that percutaneous electrical stimulation is safe and effective in reducing post-stroke shoulder pain, with sustained pain reduction in a cohort of subjects to at least 12 months after the end of treatment. Placement of leads in proximity to peripheral nerves within target muscles bypasses cutaneous pain receptors, which minimizes the discomfort of stimulation and ensures stable electrode placement. Further, once placed, skilled personnel are not needed on a daily basis to place electrodes to ensure effective positioning.

In an IRB approved Non Significant Risk (NSR) study, eight chronic stroke survivors with post-stroke shoulder pain, five with subluxation and three without, received three weeks of peripheral nerve electrical stimulation, 6-hrs daily via a single Smartpatch Lead placed between the motor points of the middle and posterior deltoids, which produced strong contractions of both muscles. The primary outcome measure was pain intensity (BPI 3) on the short form of the BPI. Longitudinal analysis demonstrated that participants experienced significant reduction in pain intensity. Participants also experienced significant reduction in pain interference with daily activities based on BPI 9 (F=5.9, p<0.01), and significant improvement in QoL based on the bodily pain component of the SF-36 (F=12.8, p<0.001). All 8 participants exhibited significant pain reduction at EOT. This study indicated that the threeweek, single-lead approach produced pain relief comparable to the more complex six week, 4-lead approach. The three participants without subluxation all exhibited substantial pain reduction, which reinforced that pain reduction is not mediated by improvements in subluxation and that subluxation is the not a necessary inclusion criterion.

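### Exit-site granuloma is classed as rare (1% or less), but the only counts in the protocol, 5 of 128 leads, give a point estimate in its uncommon class

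*Protocol*

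**What the plan says.** Section 10.5 sets the scale to be used: "Identify risks as common (greater than 10%) uncommon (greater than 1% up to and including 10 %) rare (1% or less". It adds, of the risk list, "This must match the risks listed in the Consent Form".

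Item 2 of that list covers the lead exit site and includes "granuloma formation (mild tissue inflammation) at the Lead exit site. Symptoms include redness, swelling, or pain". It then assigns the classes: "The risk of skin irritation is common while the risks of infection and granuloma formation are rare". Section 21.24, item 2, carries the same sentence. Item 3 of section 10.5 classes lead breakage beneath the skin as uncommon.

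Section 21.21 summarizes the prior multi-center randomized trial. Its 32 treated subjects each had four leads identical to the one used here (the system has since been renamed), left in for seven weeks. The event is described in almost the same terms: "Granuloma formation defined as localized tissue inflammation exhibited by redness, swelling, or pain at the lead exit site". It "was noted for five leads (3.9%) in two subjects (6.3", the last figure being the percentage of the 32 subjects. No lead became infected. All granulomas resolved once the leads were out, with nothing further needed. Five lead tips, also 3.9% of the 128, broke during removal.

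In the present trial every participant, including those in the sham-PNS arm, receives a single lead for four weeks.

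**The concern.** The protocol fixes numerical limits for its risk words and reports a count for this event, and the two do not agree. A rate of 3.9% is nearly four times the upper limit of rare. The inconsistency is also internal: the same 5 of 128 leads is treated as uncommon for breakage and rare for granuloma.

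What is at stake is the accuracy of a disclosed risk. Section 10.5 requires its list to match the consent form, and section 3.B.1 of the safety monitoring plan says that its anticipated adverse events are drawn from 10.5. A wrong class in 10.5 would be expected to carry into both. No endpoint, analysis or sample size depends on it.

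**Working it through.** **Inputs.** From section 21.21: 32 subjects, four leads each, seven weeks, granuloma at 5 leads in 2 subjects, breakage of 5 leads. From section 10.5: one lead, four weeks, rare at 1% or less, uncommon above 1% to 10%. From section 8.4: 96 participants.

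**1. Reproduce the protocol's figures.** 32 × 4 = 128 leads. Per lead: 5/128 = 3.91%. Per subject: 2/32 = 6.25%. Both agree with section 21.21.

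**2. Choose the rate that fits one lead.** The per-subject rate is the chance of any granuloma among four leads. For one lead the expected risk is the per-lead rate, however the events cluster: 2/32 of subjects were affected, and in them 5 of 8 leads, so 2/32 × 5/8 = 5/128 = 3.9%. This treats the average lead in the prior trial as representative of the single deltoid lead here.

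**3. Allow for the shorter indwelling time (assumption).** Linear scaling: 3.91% × 4/7 = 2.23%. Constant hazard: 1 − (1 − 0.0391)^(4/7) = 2.25%. If granulomas arise early, the figure lies between these and 3.9%. If they arise late, it is lower. Onset times are not reported. Two of the five arising within four weeks would give 2/128 = 1.6%; one of the five would give 1/128 = 0.8%.

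**4. Uncertainty if leads were independent.** The exact 95% interval for 5/128 is 1.3% to 8.9%, which excludes 1%.

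**5. Uncertainty with clustering.** Five affected leads in two subjects with four leads each can only be split 4+1 or 3+2. With y the number of affected leads in a subject and p = 5/128, the standard error is √[(32/31) Σ(y − 4p)²]/128. The design effect is its square divided by p(1 − p)/128, and the effective sample size is 128 divided by the design effect.

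| Split | Standard error | Design effect | Effective leads | Exact-type 95% interval |
|---|---|---|---|---|
| 4+1 | 3.20% | 3.5 | 36.7 | 0.3% to 16.1% |
| 3+2 | 2.77% | 2.6 | 48.8 | 0.4% to 13.8% |

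Both intervals include 1%.

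**6. What it would take to reach rare.** Five granulomas give 1% or less only over at least 5/0.01 = 500 leads. Adding the eight-subject single-lead study and the three further users in section 21.21, and assuming one lead each and no granuloma, gives 5/(128 + 8 + 3) = 5/139 = 3.6%.

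**7. Size in this trial.** With 96 participants and one lead each: 96 × 3.91% = 3.75 cases, or 96 × 2.23% = 2.14, against at most 96 × 1% = 0.96 under rare.

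**The case against.** The strongest defence is that exposure differs. The prior trial placed leads in four muscles, including supraspinatus and upper trapezius, for seven weeks; this trial places one in the deltoid for four. The documents give no counts by muscle and no onset times, so a true single-lead, four-week rate at or below 1% is possible, as step 3 shows. That stands. It is a reason for the protocol to state why it chose rare, and no such basis appears in the text available.

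A second defence is that 128 leads are not the whole experience. Section 10.5, item 4, refers to hundreds of leads over 30 years, but gives no counts, and its own summary is "Infections and granulomas of leads or lead fragments have been uncommon". That sentence should not be pressed as support either. It sits under fragment-related infection and pools infection with granuloma, so on the defined scale it would count equally against rare for infection.

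Third, some text beside item 2, the matching entry in 3.B.1 and the consent form are not in the copy reviewed. A reader might infer that participants have been told rare. That is likely from the matching rule, but it cannot be seen.

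A reader might also infer that cases at the prior rate would look abnormal to the safety board. The documents do not support this. Granuloma is a listed risk, section 6.10 sorts events as expected or unexpected without a frequency trigger, and at a true 1% rate two or more cases in 96 would occur with probability 1 − 0.99^96 − 96 × 0.01 × 0.99^95, about 25%.

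**Conclusion.** The inconsistency holds. On the protocol's own scale, the class given to exit-site granuloma conflicts with the only counts it reports. The point estimate is 3.9% per lead, or about 2.2% after linear scaling to four weeks, and both are uncommon. The first assumes that the average prior lead represents the deltoid lead used here; the second also assumes that risk is proportional to indwelling time.

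Two stronger readings do not hold. One is that the risk is 6.3%: that rate belongs to four leads over seven weeks. The other is that the true risk has been shown to exceed 1%: all events came from two people, and the clustered intervals start at 0.3% to 0.4%.

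The point is limited to granuloma. With no infection in 128 leads, section 21.21 does not contradict rare for infection. Severity is minor: the protocol describes the event as mild, every case resolved after lead removal without further intervention, and removal at four weeks is already planned.

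**What to change.** Reclassify exit-site granuloma as uncommon in sections 10.5 and 21.24, item 2 in each. Check section 3.B.1 and the consent form, and change them if they carry the same label. List infection as a separate entry, so that one class does not cover two events with different records. Alternatively, keep rare, but state the data that support it for one deltoid lead over four weeks and reconcile them with the 5 of 128 leads in section 21.21.

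The cost is a wording change in two to four places and, if the consent form is affected, a consent revision. The stated risk becomes slightly less favorable. Design, conduct and analysis are unchanged.
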